6. High-degree cardiac arrhythmia, including atrial fibrillation and severe atrioventricular block
7. Use of cardiac pacemaker or automated implantable cardioverter defibrillator
8. Chronic kidney disease, stage ≥ 4 (estimated glomerular filtration rate $< 30 \text{ ml}\cdot\text{min}^{-1}$)
9. Planned transferal to intensive care unit for mechanical ventilation
10. QTc prolongation determined by a standard 12-lead electrocardiogram
11. Patients using emetogenic or antiemetic drugs within 24 hours before surgery
12. Patients requiring rapid sequence induction or fiberoptic awake intubation
13. Patient refusal to participate

The flow diagram for research conduction is shown in Figure 2. Before surgery, all participants will be evaluated for morphometric and airway characteristics regarding difficult airway, including interincisor distance (< 3 cm or not)⁴³, mentohyoid distance (< 4 cm or not), thyromental distance (< 6.5 cm or not)⁴⁴, neck movement (< 80 degrees or not)⁴⁵, neck circumference measured at the thyroid cartilage (> 43 cm or not)⁴⁶, modified Mallampati score⁴⁷, upper lip bite test⁴⁸, and mandibular prognathism test⁴⁹.

[figure not shown]

Figure 2: Flow diagram for research conduction

Substudy 1: An evaluation of the effect of intravenous dexamethasone on postoperative nausea and vomiting: a double-blind, placebo-controlled trial

At the operating room, patients will be initially placed in a ramped position and then moved into a reverse Trendelenburg position to achieve a 30-degree incline of the thorax before preoxygenation. Each patient will be randomly assigned 1:1, stratified by presence of diabetes mellitus, to one of each of the following two interventions: dexamethasone (8 mg intravenously) and placebo (0.9% sodium chloride). The envelopes of group allocation will be opened just before the induction of general anesthesia.

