Primary outcome is the incidence of PONV, which includes any nausea, emetic episodes (retching or vomiting), or both during the first 24 postoperative hour. At the 2nd and 24th postoperative hours, trained investigators who are blinded to the group allocation will record the number of emetic episodes, the time each one occurs, and self-reported worst nausea episode during the preceding duration on an 11-point scale (0: no nausea and 10: the most severe nausea). Secondary outcomes are serum glucose levels of post-induction, end of surgery, and the 24th postoperative hour. We will also evaluate risk factors for PONV according to Apfel risk prediction model, including age, sex, smoking status, body mass index, history of PONV or motion sickness, duration of anesthesia, and the use of intraoperative and postoperative intravenous opioids. Research staff blinded to group allocation will determine and document any episodes of surgical site infection and delayed wound healing within 30 days after surgery.

Substudy 2: An investigation of the threshold inspiratory pressure for gastric insufflation using ultrasonography of gastric antrum: a double-blind randomized controlled trial

We will measure the antral area of each participant lying in supine position on the operating table, using a portable ultrasound device (LOGIQ™, GE Healthcare, Chicago, IL, USA, fitted with a 1.5 to 5.0 MHz convex transducer). We will determine the longitudinal (D₁) and anteroposterior (D₂) diameters of the cross-section of antrum in the sagittal plane passing through abdominal aorta.⁵⁰ To obtain a standardized scanning level, the aorta and left lobe of the liver are employed as internal landmarks. The relaxed diameters of the antrum are measured between antral contractions. The area of gastric antrum is calculated using the formula: antral area = D₁×D₂×π / 4. In addition, the gastric fluid volume will be calculated with a validated model based on the cross-sectional area of the gastric antrum, described previously.⁵¹

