According to prior study⁶⁴, at least 80 patients in each group of GDHT and control are needed to detect a significant difference, accepting a type I error of 5% and type II error of 10% with anticipated incidence of postoperative major complications 30% in GDHT group and 55% in control group in Substudy 4.⁶⁵ To allocate 60 subjects to each group of video intubating stylet, video laryngoscopy, and direct laryngoscopy in Substudy 3, a total of 180 subjects are needed for the factorial trial. There are about 120 obese people undergoing LSG at our hospital per year. Considering the patient selection criteria and possible patient refusal, an estimated sample of 90 patients will be recruited per year in this trial. Therefore, it will take about 2 years for patient recruitment.

Statistical Analysis

Baseline patient characteristics and outcome variables will be compared between two groups using chi-square tests or Fisher's exact tests for categorical variables and either t tests or Wilcoxon rank sum tests for continuous variables, as appropriate. For three and four group comparisons, chi-square tests or Fisher's exact tests will be used for categorical variables and either one-way ANOVA or Kruskal-Wallis rank test for continuous variables, as appropriate. *Post hoc* pairwise comparisons will be performed using the Bonferroni correction. For longitudinal data, generalized linear mixed models or generalized estimating equations models will be used to analyze the association between exposure variables and outcomes of interest. For time to event data, Kaplan-Meier method and log-rank test will be applied for group comparisons. Multivariable logistic regression, simple linear regression, or Cox proportional hazards regression analyses will be used to identify potential influential factors of outcomes. A two-sided significance level of 0.05 will be used to define statistically significant difference. All the statistical analyses will be conducted using Statistics Analysis System (SAS), Version 9.4 (SAS Institute Inc., Cary, NC, USA).

References

1. World Health Organization. Fact sheets: Obesity and overweight. <https://www.who.int/en/news-room/fact-sheets/detail/obesity-and-overweight> (accessed on December 5, 2020).
2. Blüher M. Obesity: global epidemiology and pathogenesis. *Nat Rev Endocrinol.* 2019;15:288-98.

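### The primary PONV comparison in Substudy 1 is a valid but unadjusted test that leaves unused the diabetes stratum and the baseline PONV predictors the trial already collects

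*Combined protocol and SAP*

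**What the plan says.** All of this is in the combined protocol and SAP.

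- **Allocation (Substudy 1).** "Each patient will be randomly assigned 1:1, stratified by presence of diabetes mellitus, to one of each of the following two interventions". Diabetes is the only stratification factor. Envelopes are opened just before induction, and study drug follows within 10 minutes after it.
- **Primary outcome (Substudy 1).** "Primary outcome is the incidence of PONV, which includes any nausea, emetic episodes (retching or vomiting), or both during the first 24 postoperative hour".
- **Risk factors (Substudy 1).** "We will also evaluate risk factors for PONV according to Apfel risk prediction model", then a list whose last item is opioid use: "including age, sex, smoking status, body mass index, history of PONV or motion sickness, duration of anesthesia, and the use of intraoperative and postoperative intravenous". Diabetes is not on it. How these factors enter the treatment comparison is not stated.
- **Secondary outcome (Substudy 1).** "Secondary outcomes are serum glucose levels of post-induction, end of surgery, and the 24th postoperative hour".
- **Two-group comparison (Statistical Analysis).** "outcome variables will be compared between two groups using chi-square tests or Fisher's exact tests for categorical variables". No covariate or stratum is mentioned.
- **Regression (Statistical Analysis).** "Multivariable logistic regression, simple linear regression, or Cox proportional hazards regression analyses will be used to identify potential influential factors of outcomes". No covariates are named, and the sentence does not say that the model estimates the dexamethasone effect.
- **Size (Sample Size Estimation).** 180 patients in total, so about 90 per arm in Substudy 1. The only power calculation is for Substudy 4.

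**The concern.** Eligibility does not restrict baseline PONV risk; the exclusion that touches PONV covers only recent emetogenic or antiemetic drugs. The background section gives PONV rates of 18% to 82% after bariatric surgery and a higher risk in morbid obesity. The patients are therefore likely to vary in PONV risk, and the trial records the factors it regards as predictive. A chi-square or Fisher's exact test treats all of that variation as noise.

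Two things are at stake. The first is power, in a substudy with no sample-size calculation and so no stated margin. The second is clarity. The plan offers an unadjusted test and a regression with open covariates and does not rank them for the PONV result. The risk-factor list also mixes baseline items with items that arise after allocation, so a later analyst has no written guide to which belong in a model for the treatment effect.

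**Working it through.** **1. The plan's own figure.** The only one is Substudy 4's 80 per group (30% vs 55%, two-sided 5%, 90% power). With pooled p = 0.425:

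n = [1.96·√(2·0.425·0.575) + 1.2816·√(0.30·0.70 + 0.55·0.45)]² / 0.25² = (1.370 + 0.867)² / 0.0625 ≈ 80.1

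Rounded up this is 81, and power at 80 per group is 0.8997. The figure reproduces, but it says nothing about PONV.

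**2. Size of chance imbalance.** For a binary baseline factor with prevalence p and 90 per arm, the SD of the between-arm difference is √(2p(1−p)/90). The prevalences are assumptions.

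| p | SD (points) | P(gap ≥ 10 points) |
|---|---|---|
| 0.40 | 7.3 | 0.17 |
| 0.65 | 7.1 | 0.16 |
| 0.75 | 6.5 | 0.12 |

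If these three factors are independent, at least one such gap occurs with probability 1 − 0.83·0.84·0.88 ≈ 0.39. The effect of one gap is small. Near a 50% event rate, an odds ratio of 2 to 2.5 is a risk difference of about ln(2)/4 = 0.17 to ln(2.5)/4 = 0.23. A 10-point gap therefore moves the PONV difference by about 1.7 to 2.3 points. A treatment odds ratio of 0.42 at 50% control PONV gives odds of 0.42, a rate of 0.42/1.42 = 0.30, and so an effect of about 20 points. The standard error of the unadjusted test already allows for such gaps.

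**3. Power given up.** Simulated trials of 180 patients, three binary baseline factors (prevalences 65%, 75%, 40%), two-sided 5%. All inputs other than the trial size and alpha are assumptions.

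*Adjusting for a risk count; treatment odds ratio 0.42; 4,000 trials per row:*

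| Odds ratio per factor | Control PONV | Unadjusted | Adjusted | Gain (points) |
|---|---|---|---|---|
| 1.5 | 50% | 79.2% | 79.7% | 0.6 |
| 1.5 | 60% | 79.0% | 81.2% | 2.2 |
| 2.0 | 50% | 75.7% | 77.6% | 2.0 |
| 2.0 | 60% | 75.4% | 79.1% | 3.7 |
| 2.5 | 50% | 71.6% | 75.4% | 3.7 |
| 2.5 | 60% | 71.0% | 77.0% | 6.0 |

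Gains are taken before rounding. The simulation error of each power is about √(0.77·0.23/4000) = 0.7 points, so 0 to 7 points is a fair summary.

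*Adjusting for the three factors separately; treatment odds ratio 0.4; 3,000 trials per scenario:* with factor odds ratios from (2, 1.6, 2) to (3, 2, 3) and control PONV of 30–70%, unadjusted power was 64–81% and adjusted power 68–82%. Gains ran from 0.2 to 4.9 points.

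The simulated models had no diabetes term, because the documents give no link between diabetes and PONV.

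**4. Validity.** With no treatment effect, rejection rates in the second set were 3.6–5.4% unadjusted and 4.6–6.0% adjusted. Both are near 5%.

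**5. Timing of the listed factors.** Age, sex, smoking, body mass index and PONV or motion-sickness history precede allocation. Anesthesia duration and intraoperative and postoperative opioid use follow the opening of the envelope.

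**The case against.** The case for leaving the plan alone is substantial, and much of it stands.

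- **A reader might infer that the arms are unbalanced or the estimate biased.** The documents do not support that. Permuted-block 1:1 randomisation balances every baseline factor in expectation. Only enforced balance on the PONV predictors is absent, and the unadjusted test keeps its error rate.
- **A reader might infer that diabetes is the wrong stratifier.** It is not. The first research objective covers adverse effects as well as effectiveness, the background raises hyperglycemia and wound problems, and glucose is a secondary outcome. A stratifier need not predict the primary outcome.
- **A reader might infer that a PONV-risk stratum is needed.** When one was simulated on top of adjustment, power changed by −2 to +2.5 points, with no consistent sign and close to simulation noise.
- **A reader might infer that the plan adjusts the treatment effect for duration and opioids.** It does not say so. Evaluating them as risk factors is a legitimate exploratory aim.
- **The gain is small and rests on assumed inputs.** This is true. At the weakest predictors it is close to nil.
- **Logistic regression is already planned.** It is, but for finding influential factors, with no covariates named and no role in the primary comparison. This objection does not close the gap.

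**Conclusion.** The point holds as one of efficiency and pre-specification. The planned PONV test is sound, but it discards the diabetes stratum and baseline information already in hand. At 90 per arm the cost is about 0 to 7 points of power, given factor prevalences of 40–75%, odds ratios of 1.5–2.5 per factor, control PONV of 50–60% and a treatment odds ratio of 0.42. Weaker predictors would put the gain at the bottom of that range. None of these inputs comes from the documents, which set no PONV rate or effect for Substudy 1. The change is worth making because it costs almost nothing; the present test is not invalid.

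**What to change.** Change the analysis text only. Keep the diabetes stratification and the randomisation list as they are.

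1. State that the primary PONV analysis is a logistic regression with treatment, the diabetes stratum and a baseline risk count: one point each for female sex, non-smoker, and history of PONV or motion sickness. Confirm the scoring against the risk model the protocol cites, and fix it before unblinding.
2. Keep the chi-square or Fisher's exact test as a sensitivity analysis.
3. State that anesthesia duration and intraoperative and postoperative opioid use are not covariates for the treatment effect. They may stay in the exploratory risk-factor analysis.
4. Report a standardised risk difference with its confidence interval beside the odds ratio.

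The cost is a few sentences; every variable is already collected. The one small drawback is that the adjusted odds ratio is conditional on the covariates and not directly comparable with a crude one, which is why item 4 is there.

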2. Investigation of perioperative use of dexamethasone will enrich the current literature of PONV prophylaxis for obese patients.
3. The study will determine the airway pressure threshold to prompt gastric insufflation during positive ventilation, providing a practical guidance in the airway management of anesthesia and cardiopulmonary resuscitation.
4. This study will evaluate the application of video intubating stylet in the tracheal intubation of obese patients, offering another evidence-based intubation technique.
5. This research will also provide valuable evidence regarding the treatment effect of intraoperative GDHT in obese patients, which may offer an important implication for precision hemodynamic management in the obese people.
6. The study will provide important evidence for an Enhanced Recovery After Surgery (ERAS) protocol of bariatric surgery.

Materials and Methods

We will conduct a factorial parallel randomized controlled trial using permuted block randomization and stratified randomization and conforming to the CONSORT Statement to investigate multiple clinical outcomes in obese patients undergoing laparoscopic sleeve gastrectomy (LSG) at Shuang Ho Hospital, Taipei Medical University, New Taipei City, Taiwan.⁴⁰⁻⁴² Four randomizations will be conducted, including intravenous dexamethasone for PONV, various inspiratory pressure of mask ventilation, three tracheal intubation techniques, and goal-directed hemodynamic therapy using minimally invasive cardiac output monitoring. (Figure 2) A computer-generated list of randomizations will be applied for these group allocations. Each patient will be randomly assigned a specific study number and group in four randomizations, and these assignments will be then enclosed in envelopes and sealed.

Inclusion criteria are patients aged ≥ 20 years with body mass index $\geq 30 \text{ kg}\cdot\text{m}^{-2}$ undergoing LSG at Shuang Ho Hospital. Exclusion criteria are as the following:

1. Pregnant or lactating women
2. Severe cardiopulmonary distress, including left ventricular ejection fraction $< 40\%$, double or triple vessel disease, New York Heart Association functional classification ≥ 3 , peripheral oxygen saturation by pulse oximetry (SpO_2) $< 90\%$ in room air, and moderate to severe pulmonary hypertension.
3. Previous esophageal, gastric, or duodenal surgery.
4. Previous head and neck surgery or radiation therapy
5. Previous cervical spine injury

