After preoxygenation using facemask with pure oxygen $10\text{ l}\cdot\text{min}^{-1}$ until end-tidal fractional oxygen concentration in the expired air (EtO_2) $\geq 80\%$, general anesthesia will be induced with propofol $1.5\text{--}2.0\text{ mg}\cdot\text{kg}^{-1}$ ideal body weight and fentanyl $1\text{--}2\text{ }\mu\text{g}\cdot\text{kg}^{-1}$ total body weight. Tracheal intubation will be facilitated with rocuronium $0.8\text{--}1.0\text{ mg}\cdot\text{kg}^{-1}$ ideal body weight. After induction, a radial artery catheterization will be performed for continuous monitoring of arterial pressure and measurement of serum glucose. In the designated patients, 8 mg of dexamethasone or placebo will be given intravenously within 10 minutes after the induction of anesthesia. Anesthesia will be maintained with 2–3 vol% sevoflurane and 60% oxygen in nitrogen, whereas the fraction of inspired oxygen (FiO_2) 0.8–1.0 will be used during pneumoperitoneum to ensure oxygen saturation higher than 92%. If the value of surgical pleth index (CARESCAPE B650 Monitor, GE Healthcare, Chicago, IL, USA) is more than 50 or heart rate or blood pressure increases by more than 20% from baseline values during surgery, an intravenous bolus of fentanyl 25 or 50 μg will be given. Besides, the concentration of sevoflurane can be adjusted as clinically appropriate.

After surgery, all patients will receive supplemental oxygen, and pain will be relieved with ketorolac 15 to 30 mg. The need for postoperative opioids will be at the discretion of the anesthesiologist, and the dose will be adjusted according to clinical needs. Patients who request rescue antiemetic therapy or who have an emetic episode will be given droperidol 1.25 mg. If symptoms persist, metoclopramide 10 mg will be administered.

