Primary outcome is the best glottis visualization, graded according to Cormack and Lehane's classification with external laryngeal pressure applied.⁵⁷ Glottic views graded as III or IV are regarded as difficult. Secondary outcomes are number of intubation attempts, the percentage of glottic opening (POGO) score, time to intubation, lowest SpO_2 during intubation, and ease of intubation. Each video stylet or laryngoscope blade insertion is defined as an intubation attempt. Minor adjustments of patient's position or tube stylet are not considered separate attempts. The POGO score is defined by the best glottis visualization (0%, 25%, 50%, 75%, or 100%).⁵⁸ Time to intubation is defined as the interval between intubating stylet or laryngoscope insertion into oral cavity and EtCO_2 detected. Ease of intubation is a subjective assessment of anesthesiologists, rated as (1) very easy, (2) easy, (3) moderate, (4) difficult, and (5) impossible.⁵⁹ Safety outcomes are upper airway injury (bleeding, abrasion or laceration), dental injury (bleeding, trauma, fracture), respiratory complications (laryngospasm, bronchospasm, aspiration), cough (mild, moderate, severe), sore throat (mild, moderate, severe), and hoarseness (noticed by the patient only, apparent to an observer). Research staff blinded to group allocation will evaluate the complications at the 2nd and 24th postoperative hours.

Substudy 4: An investigation of the putative benefits of goal-directed hemodynamic therapy targeting cardiac index in obese patients undergoing laparoscopic sleeve gastrectomy: an open-label randomized controlled trial

At the operation room, we will apply the Masimo Radical 7 pulse oximetry (Masimo Corp., Irvine, CA, USA) to the fingers of all enrolled patients to measure perfusion index and SpO₂ throughout the surgery. After the placement of a tracheal tube, patients will receive ventilator support with the tidal volume 6–8 ml·kg⁻¹ ideal body weight, a respiratory rate of 10–15 min⁻¹ and PEEP 5 cmH₂O applied by the ventilator.⁶⁰ The FiO₂ will be set at 0.3–0.7 to maintain SpO₂ ≥ 98% throughout the surgery. Each patient will be randomly allocated to one of each of the following two groups: goal-directed hemodynamic therapy and control.

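### During pneumoperitoneum every patient is under two inspired-oxygen ranges that do not overlap: 0.8–1.0 in Substudy 1 and 0.3–0.7 in Substudy 4

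*Combined protocol and SAP*

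**What the plan says.** Two places in the combined protocol and SAP set FiO2 during surgery.

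- **Substudy 1, conduct of anesthesia.** Maintenance uses sevoflurane with "60% oxygen in nitrogen". The same sentence then makes a contrast for one phase: FiO2 "0.8–1.0 will be used during pneumoperitoneum to ensure oxygen saturation higher than 92" per cent.
- **Substudy 4, ventilator settings after intubation.** FiO2 "will be set at 0.3–0.7 to maintain SpO₂ ≥ 98% throughout the surgery". This text comes before the allocation to goal-directed hemodynamic therapy (GDHT) or control and is not limited to either arm.

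The plan puts the same patients under both texts. Materials and Methods states: "Each patient will be randomly assigned a specific study number and group in four randomizations". Substudy 1 states: "Each patient will be randomly assigned 1:1, stratified by presence of diabetes mellitus". Substudy 4 states: "Each patient will be randomly allocated to one of each of the following two groups: goal-directed hemodynamic therapy and control". Substudy 4 also applies the pulse oximeter "to the fingers of all enrolled patients to measure perfusion index and SpO₂ throughout the surgery". Sample Size Estimation gives the number: "a total of 180 subjects are needed for the factorial trial".

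**The concern.** The substudies are written as if each had its own conduct section, but the design is factorial and each patient follows all of them. Where two conduct sections set the same ventilator parameter, they have to agree. For pneumoperitoneum they do not, and nothing in the visible text gives one precedence.

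The first consequence is practical: staff cannot comply with both instructions, so a protocol deviation is built into every operation. The second is statistical. SpO2 is a longitudinal secondary outcome of Substudy 4. If anesthesiologists resolve the conflict in different ways, FiO2 in this phase will vary more than either passage intends, and some of that variation could reach the SpO2 readings taken then.

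**Working it through.** The plan states no figure to reproduce here. The check compares two intervals and asks whether they bind the same patients at the same time.

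**1. Same patients.** Materials and Methods gives each patient a group in all four randomizations, and Substudies 1 and 4 each say that each patient is allocated. Neither FiO2 statement is restricted to an arm or subset. Both therefore apply to all 180 planned patients.

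**2. Same time.** Substudy 4 covers the whole operation. Its data schedule includes a reading 5 min after the start of pneumoperitoneum, so that phase is inside its scope.

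**3. Overlap.** Two ranges overlap only if the larger lower limit does not exceed the smaller upper limit.

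- Substudy 1, pneumoperitoneum: 0.8 to 1.0
- Substudy 4, whole surgery: 0.3 to 0.7
- Larger lower limit: 0.8. Smaller upper limit: 0.7. Since 0.8 > 0.7, there is no overlap.
- Gap: 0.8 − 0.7 = 0.1

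**4. Other phases.** The 60% maintenance setting in Substudy 1 is 0.60, which lies within 0.3 to 0.7. The conflict is confined to pneumoperitoneum.

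**5. Saturation floors.** The floors attached to the two ranges are above 92% and at least 98%. A reading of 98% or more meets both, so the floors differ but do not contradict each other.

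**6. Range of settings that comply with at least one passage.**

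| Quantity | Arithmetic | Result |
|---|---|---|
| Width, Substudy 4 text alone | 0.7 − 0.3 | 0.4 |
| Width, Substudy 1 text alone | 1.0 − 0.8 | 0.2 |
| Outer span, either text | 1.0 − 0.3 | 0.7 |
| Added to the span, against Substudy 4 alone | 0.7 − 0.4 | 0.3 |
| Added to the span, against Substudy 1 alone | 0.7 − 0.2 | 0.5 |
| Total width of permitted settings, leaving out the 0.7–0.8 gap | 0.4 + 0.2 | 0.6 |

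The outer span includes the gap, where neither passage is met. Without the gap, the contradiction adds 0.6 − 0.4 = 0.2 or 0.6 − 0.2 = 0.4 of permitted settings. Each passage alone already allows a range, so only the added part is due to the contradiction.

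**7. Exposure of the outcomes.** Substudy 4 schedules five SpO2 readings: after induction, after the start of pneumoperitoneum, after its end, at cessation of the volatile agent, and after extubation. One of the five falls in the conflict phase. Some of the 15-min records do too, but the plan gives no duration of pneumoperitoneum, so their number cannot be stated. The PaO2/FiO2 outcome is listed with values after induction and at the end of surgery, and so appears to lie outside this phase.

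**The case against.** The strongest reply is that the Substudy 1 sentence is the specific rule for pneumoperitoneum and the Substudy 4 sentence is the general ventilator setting, so the specific rule governs. A related reading attaches the phrase about the whole surgery to the SpO2 target alone. Neither removes the conflict. The passages do not refer to each other and no precedence is stated. Even on the second reading, 0.3–0.7 remains the stated means of holding the target for the entire operation, which includes pneumoperitoneum. The study-flow and hemodynamic-algorithm figures are not available in the text and could not be checked. Their captions do not mention FiO2.

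The objection to the size of the consequence carries more weight. This is a single-hospital trial, and nothing in the documents shows that anesthesiologists would divide. If all follow the same passage, the conflict adds no variation, although every patient then deviates from the other passage. SpO2 is also held to a target, which would dampen any effect of FiO2 on it. The widths above describe permitted settings and say nothing by themselves about an outcome. All of this stands. It limits what can be claimed about the analysis, but it does not make the two instructions compatible.

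**Conclusion.** The contradiction is real. During pneumoperitoneum no FiO2 setting complies with both texts. The ranges are 0.1 apart, and all 180 planned patients fall under both. This rests only on reading both statements as unconditional, as they are worded, and on the factorial allocation of each patient.

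The demonstrated statistical effect is limited. Added variation in the SpO2 series is possible, but only if practice differs between staff. It may be small, and the documents do not allow an estimate. No primary outcome and no difference between GDHT and control is shown to be affected. The point should be fixed because the plan cannot be followed as written in a phase of every operation and the correction is cheap. It is not a threat to the main comparisons.

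**What to change.** Reconcile the Substudy 1 and Substudy 4 texts so that a single FiO2 instruction applies during pneumoperitoneum to all patients and to both GDHT arms. The choice belongs to the clinical team, and this review takes no view on it. Since each saturation floor is tied to one of the two ranges, the revised text should also say how the two floors relate.

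As an option, record the FiO2 in use beside each SpO2 reading if the anesthesia record does not already hold it. The PaO2/FiO2 outcome already needs FiO2 at the blood-gas times.

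The cost is a wording change, a notice to staff and at most one data field. Sample size, randomization and the analysis methods are unaffected.

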Substudy 3: A comparison of video intubation stylet and video laryngoscope in tracheal intubation: an open-label randomized controlled trial

Eligible patients will be randomly allocated 1:1:1, stratified by body mass index $> 50 \text{ kg}\cdot\text{m}^{-2}$, to group 1 (video intubating stylet), group 2 (video laryngoscopy), or group 3 (direct laryngoscopy). Tracheal intubation will be performed by experienced attending anesthesiologists who have performed at least 100 cases each with Trachway® video intubating stylet, GlideScope® video laryngoscopy, and Macintosh direct laryngoscopy. The anesthesiologist performing tracheal intubation is blinded to all preoperative evaluations.

In group 1, a tracheal tube (ConvaTec, Berkshire, England, UK) in appropriate sizes is preloaded over the Trachway® video intubating stylet (TVI-4050, Markstein Sichtec Medical Corp, Taichung, Taiwan), which is introduced into oral cavity to visualize the epiglottis and guided to glottis via a monitor after full neuromuscular blockade is achieved. In group 2, a tracheal tube is preloaded over a GlideRite® stylet, which is specifically designed to work with GlideScope® video laryngoscope (Verathon Medical, Bothell, WA, USA). GlideScope® blade size 3 (GS-3) or 4 (GS-4) is used in all patients. In group 3, tracheal tubes are prepared with a hockey stick-shaped stylet, and direct laryngoscopy is performed using a size-3 or -4 Macintosh blade (Rüsch Inc., Duluth, GA, USA). In all patients, backward, upward, and rightward pressure on the larynx and Sellick maneuvers are allowable to obtain the best glottic view.^{55,56} If the initial intubation attempt fails or is terminated for desaturation (defined as $\text{SpO}_2 < 92\%$) or need to change the patient's position, the intubation device will be removed, and manual bag mask ventilation will be performed. Intubation failure is defined as more than three intubation attempts or need to change intubation devices. Any intubation rescue techniques will be used at the discretion of the staff anesthesiologist.

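### Substudy 3 counts an intubation attempt by insertion of the viewing device, which carries the tube in the video-stylet arm only, so repeat tube passes can go uncounted in the two laryngoscope arms.

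*Combined protocol and SAP*

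**What the plan says.** All of this is in the Substudy 3 section of the combined protocol and SAP.

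- Counting unit: "Each video stylet or laryngoscope blade insertion is defined as an intubation attempt".
- Exemption: "Minor adjustments of patient's position or tube stylet are not considered separate attempts".
- Group 1: the tube "in appropriate sizes is preloaded over the Trachway® video intubating stylet", so the viewing device and the tube carrier are one object.
- Group 2: "In group 2, a tracheal tube is preloaded over a GlideRite® stylet"; the GlideScope blade gives the view.
- Group 3: "In group 3, tracheal tubes are prepared with a hockey stick-shaped stylet"; the Macintosh blade gives the view.
- After a failed or terminated initial attempt, in any arm: "the intubation device will be removed, and manual bag mask ventilation will be performed".
- Failure: "Intubation failure is defined as more than three intubation attempts or need to change intubation devices".

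The number of attempts is the first-listed secondary outcome. The primary outcome is the best Cormack-Lehane view. Intubation failure is defined but is not among the listed outcomes. Sample Size Estimation gives 60 patients per arm and no effect size or power for this substudy. Statistical Analysis plans chi-square or Fisher tests for categorical variables across three groups, then Bonferroni-corrected pairwise comparisons, at a two-sided 0.05.

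**The concern.** The counted event is not the same physical event in the three arms. Under a laryngoscope blade, the operator can withdraw the tube, reshape its stylet and pass it again without a new blade insertion. Read literally, the count stays at one, and the exemption for tube-stylet adjustments supports that reading. In group 1, withdrawing the tube from the mouth withdraws the viewing stylet, and the next pass is a new insertion.

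Research Objective 3 asks how the video stylet compares with the video laryngoscope in effectiveness and safety, and the attempt count is part of that evidence. The substudy is open-label, so operators and recorders would settle the undefined case with the device known to them. Tube passes that are not recorded at the time may not be recoverable later.

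**Working it through.** The documents give no attempt rate, per-pass success rate or power for Substudy 3, so there is no stated figure to reproduce. The check is a reading of the text and then an illustration.

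**Step 1. The same event under each reading of the text**

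| Event | Group 1 (stylet) | Groups 2 and 3 (blade) |
|---|---|---|
| Redirected without leaving the mouth | no new attempt | no new attempt |
| Tube withdrawn, blade left in place | cannot occur: the device comes out, so re-entry is a new attempt | no new insertion, so not counted, unless a failed pass is a failed attempt |
| Failed pass treated as a failed attempt, device removed | new attempt | new attempt |
| Blade exchanged between size 3 and size 4 | does not arise | new attempt |

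The second row favours the laryngoscopes, the third is neutral, and the fourth works against the laryngoscopes. The text does not say how a failed pass moves between rows two and three.

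**Step 2. Illustration**

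Inputs from the documents: 60 per arm, two-sided 0.05, and Bonferroni over three pairs, so 0.05/3 = 0.0167.

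Assumptions, not in the documents: the same per-pass success p in all arms; two passes possible under one blade insertion; and either every failed stylet pass, or half of them, requires removal. The count is reduced to success on the first attempt, which is a simplification of the planned outcome.

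- Blade: 1 − (1 − p)². For p = 0.8 this is 1 − 0.04 = 0.96; for p = 0.9 it is 1 − 0.01 = 0.99.
- Stylet, every failed pass removed: p, that is 0.80 or 0.90.
- Stylet, half of failed passes corrected in place: p + 0.5(1 − p)p. For p = 0.8 this is 0.8 + 0.08 = 0.88; for p = 0.9 it is 0.9 + 0.045 = 0.945.

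Exact binomial enumeration of one stylet-versus-laryngoscope comparison gives the chance of rejecting although the devices are equal:

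| Stylet v blade | Chi-square / Fisher at 0.05/3 | Chi-square / Fisher at 0.05, unadjusted |
|---|---|---|
| 80% v 96% | 67% / 58% | 81% / 72% |
| 90% v 99% | 40% / 27% | 63% / 40% |
| 88% v 96% | 22% / 15% | 37% / 23% |
| 94.5% v 99% | 7% / 3% | 25% / 7% |

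The 0.05/3 column matches the plan. The average expected number of patients without first-attempt success is 60 × 0.12 = 7.2 per arm in the first row, but 60 × 0.055 = 3.3, 60 × 0.08 = 4.8 and 60 × 0.0325 = 1.95 in the others. Fisher is the customary test in those three rows.

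**Step 3. Removal in every arm**

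If every failed pass leads to removal in all arms, first-attempt success is p everywhere. The unadjusted false-positive rate is then 5.0% (chi-square) or 2.2% (Fisher) at p = 0.9, and 5.0% or 2.8% at p = 0.8. The artefact disappears.

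**Step 4. The failure rule**

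More than three attempts has probability (1 − p)³ in the stylet arm when every failed pass is removed. For p = 0.8 this is 0.2³ = 0.8%, or 0.48 expected cases in 60; for p = 0.9 it is 0.1³ = 0.1%, or 0.06 cases. The blade arms have (1 − p)⁶, which is practically zero. The rule hardly moves.

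**The case against.** The strongest objection is that the removal rule after a failed attempt applies to all arms. If a failed pass is a failed attempt, the blade also comes out, its reinsertion counts, and the arms are treated alike. This stands as a possible reading, and Step 3 shows that it removes the artefact. It does not settle the matter, because an attempt is defined by insertion and nothing says that a failed pass under a retained blade ends it.

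Two further objections stand in full. Nothing in the text says that a failed pass forces the stylet out of the mouth, and a stylet redirected in place adds no attempt. A blade-size exchange counts only against the laryngoscopes. The direction is therefore likely, not fixed.

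The percentages also rest on assumed pass rates, and the unadjusted 5% pairwise figures overstate what the planned Bonferroni procedure would give.

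A reader might infer two stronger points that the documents do not support:

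- That the failure rule is materially tilted against the stylet. Under the assumptions above it adds about half an expected case or fewer in 60. Failure is not a listed outcome, and its device-change limb does not use the count.
- That the two sentences on position contradict each other. One ends an attempt on a "need to change the patient's position, the intubation device will be removed"; the other exempts minor adjustments only. Both can hold, although no threshold for a minor adjustment is given.

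**Conclusion.** The point holds as a cheap improvement to one secondary outcome. It is certain from the text that the counted event differs between the arms and that a failed tube pass under a retained blade is not classified. It is likely, but dependent on practice, that the number of attempts would be biased against the video stylet.

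The size cannot be fixed from the documents. On the assumptions shown, false rejection at the planned Bonferroni level runs from about 67% (chi-square) or 58% (Fisher) down to 7% or 3%, with no artefact if every failed pass leads to removal in all arms. The primary outcome, POGO score, time to intubation, lowest SpO₂ and ease of intubation do not use the count. Time to intubation runs from device insertion to detected EtCO₂, so repeat passes under one blade would still lengthen it.

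**What to change.** For the attempts outcome, count the same event in all three arms: each advance toward the glottis of the device that carries the tube (video stylet, GlideRite stylet or hockey-stick stylet) that ends with the tube withdrawn, or any removal of the viewing device. State that one withdrawal of tube and device together counts once, and that the advance which places the tube completes the final attempt. Record device insertions and tube passes in two separate case-report fields, so that either count can be reported.

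This changes measurement only; the clinical rule on when the device is removed stays as written. The cost is one extra case-report field and slightly less favourable counts in the laryngoscope arms.
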